7.2.4 Endorectal Brachytherapy 3D Treatment Planning

The tumor volume is defined as the (gross tumor volume=GTV). The GTV plus additional intramesorectal extension is defined as the clinical target volume=CTV (Figure 4). Adjacent normal tissues will also be contoured. The normal rectal volume is the volume confined to within 5 mm of the perimeter of the balloon that did not extend beyond 1 cm of the superior and inferior margins of the target. When a balloon is not used, the normal rectum volume will be confined to the normal rectum (non-CTV) within 5 mm of the applicator. The percentage of the CTV covered by 100% and 150% of Dref (V100 and V150), and the minimum dose received by 90% of the CTV (D90) will be calculated. The mean dose (Dmean) to normal tissues, inclusive of bladder, femoral heads, bone marrow, uterus, vagina,

prostate, penile bulb will also be calculated and included in the dose volume histogram. Bone marrow will be defined by contouring all osseous structures from the L4/L5 interspace through the sacrum, pelvis, and proximal femurs to the inferior aspect of the inferior pubic rami. The other normal structures will be defined in accordance with the RTOG male and female atlas guidelines (see Section 7.2.9). In addition, the minimum dose to the hottest 1, 2, and 5 cm³ (D1cc, D2cc, and D5cc) of the normal structures will be calculated to examine anatomic heterogeneity effects. The doses are expressed as a percentage of Dref. We will confirm that 100% of the CTV volume is covered by the 95% isodose line. Any visible perirectal lymph nodes seen on imaging will be included in the treatment volume however other mesorectal lymph nodes are not always included as it is assumed these will be removed by the TME. As a general rule, any lymph node deposits located within 0.5 and 1 cm from the target CTV will receive 75% and 50% of the prescribed dose. Endorectal markers as well as the first dwell position are incorporated into digitally reconstructed radiographs for use as a reference for the daily treatments. The digitally reconstructed radiographs will be created with the reconstruction plane set at the level of the applicator so that the ruler can be used for distance measurements between radio-opaque markers and the first dwell position of the applicator. Dwell positions are determined with respect to the extent of the contoured target. Catheters are loaded in a differential manner so that only those in close proximity with the tumor contain active source dwell positions. After the source position determination, CT-aided brachytherapy treatment planning is carried out to fully conform the dose distribution to the target, and to limit dose as much as possible to immediately adjacent tissues beyond the rectal wall.

[figure not shown]

Figure 4. Fusion of Endo-HDR CT simulation with a) MRI and b) PET/CT imaging.

7.2.5 The Differential Source Positioning Technique

Source positions for brachytherapy are determined with respect to the contoured tumor. Catheters are loaded in a differential manner so that only those in direct contact with the tumor contain active source dwell positions. Following the source position determination, CT-aided brachytherapy treatment planning is carried out so as to optimize fully the dose to the tumor, while limiting the dose to immediate adjacent tissues beyond the rectal wall. Isodose distributions were generated by Oncentra software (Nucletron USA), see dose distribution above (Figure 4b).

7.2.6 Treatment Delivery

With the patient in lithotomy position, individually marked tungsten dummies are inserted into selected channels. Prior to each treatment, AP and lateral daily check films are obtained and compared to either AP and lateral scout films or treatment planning DRRs to visualize the endorectal applicator position and orientation according to the radio-opaque endorectal markers and bony landmarks. These pre-treatment check films aid in determining both the depth and rotation of the endorectal applicator with respect to the intended position, as determined from the CT-simulation. The channel orientation is determined by the position of the dummies on check films. In the event that plain films are not available prior to a brachytherapy fraction, it is permissible to evaluate the brachytherapy applicator and plan on CT.

7.2.7 Dose Prescription

A total dose of 26 Gy in 4 daily fractions of 6.5 Gy will be prescribed at the CTV, defined as the GTV and intramesorectal deposits seen on the pre-staging MRI. The dose will be delivered with a differential channel loading of the endorectal applicator.

7.2.8 Dose Modifications

Every effort will be made to administer the entire radiation treatment to participants. Every effort will be made to limit the dose to the bladder, femoral heads, small bowel, vagina, uterus, and/or penile bulb.

7.2.9 Organs at Risk (OAR)

The following normal tissues of interest will be contoured and the dose to each recorded according to the RTOG male and female atlas guidelines:

<http://www.rtog.org/CoreLab/ContouringAtlases/MaleRTOGNormalPelvisAtlas.aspx>
<http://www.rtog.org/CoreLab/ContouringAtlases/FemaleRTOGNormalPelvisAtlas.aspx>

No part of these normal structures will be permitted to receive more than the prescription dose of 26 Gy (6.5 Gy x 4 fractions).

- All patients:
 - Small bowel, large bowel, sigmoid colon
 - Bladder
 - Femoral Heads
 - Anal sphincter
- Female patients:
 - Vagina
 - Uterus
- Male patients:
 - Prostate
 - Seminal Vesicles
 - Penile bulb

Structure	0.1 cc	2 cc
Anus*	6.5 Gy	4.8 Gy
Penile Bulb	5.9 Gy	4.8 Gy
Bladder	7.0 Gy	
Sigmoid	6.5 Gy	

Table 2. Dose Constraints for Endorectal Brachytherapy Treatment

*When the tumor approaches but does not involve the anal sphincters the dose to the anus may exceed the above constraints. Every effort should be made to limit this dose as much as possible.

7.3 Intensity Modulated Radiation Therapy and Capecitabine

7.3.1 IMRT Planning

External radiotherapy will be based on contouring guidelines from the RTOG atlas and Radiation Therapy Oncology Group (RTOG 0822) with modifications described below.

Patients will undergo CT (required) and MRI simulation (optional) in the supine position with concurrent administration of IV and oral contrast. (IV contrast may be omitted for patients with contrast allergy or another contraindication.) The bladder should be full. A custom immobilization device such as a vac-loc bag or alpha cradle should be used to ensure consistent setup. An anal BB marker should also be placed at the time of simulation.

7.3.1.1 Gross Tumor Evaluation for IMRT Treatment Planning

- GTV Primary Tumor
- Increased SUV on PET/CT will define inferior and superior aspect of tumor. Use bony anatomy to help with orientation if PET cannot be fused to planning CT.
- Use MRI to better define the anterior and posterior borders of the tumor. Again use Bony landmarks to help with orientation.
- GTV Involved Nodes
- Contour GTV for mesorectal lymph nodes which are >1cm and adjacent to the tumor (<1 cm), show enhancement on PET or MRI and/or have anatomic abnormalities suspicious for tumor involvement (based on MERCURY study).
- CTV for gross disease (per RTOG 0822)
- Primary tumor CTV = Primary Tumor GTV +1.5cm radially and 2.5cm craniocaudally
- Involved Node CTV = Involved Node GTV + 1.5cm symmetrical expansion

7.3.1.2 Clinical Treat. Vol. (CTV) & Planning Treat. Vol. (PTV) for IMRT

The RTOG Anorectal Contouring Guidelines will be used to guide treatment planning for patients in the IMRT arm of this study (50). Two PTVs will be created according to these guidelines. PTV-Initial will consist of CTVA plus margin,

including pelvic lymph nodes, the mesorectum, and the primary tumor plus margin and will receive 45 Gy in 25 1.8-Gy fractions. PTV-Conedown will include the rectal primary tumor plus margin and will receive 5.4 Gy in 3 1.8-Gy fractions. The RTOG contouring guidelines for creating target volumes are summarized below.

PTV-Initial

CTVA consists of the following areas that must always be treated in rectal cancer and will be uniformly expanded by 0.5 cm to create PTV-Initial. This volume will receive 45 Gy (1.8 Gy x 25).

- Superior border: The recommended superior extent of the peri-rectal component of CTVA was at whichever is more cephalad: the rectosigmoid junction or 2 cm proximal to the superior extent of macroscopic disease in the rectum/peri-rectal nodes. This defines how much of the distal large bowel should be within CTVA. The most cephalad extent of CTVA will be higher than the peri-rectal component, in order to properly cover the internal iliac and pre-sacral regions. The most cephalad aspect of CTVA should be where the common iliac vessels bifurcate into external/internal iliacs (approximate boney landmark: sacral promontory).
- Inferior border: Minimum 2 cm caudal to gross disease including coverage of entire mesorectum to the pelvic floor. Unless radiographic evidence of extension to ischiorectal fossa, CTVA need not extend through the levator muscles. For very advanced anal or rectal cancers, extending through the mesorectum or the levators, the group's recommendation is to add ~1-2 cm margin up to bone wherever the cancer extends beyond the usual compartments. An MRI and/or PET/CT scan is strongly recommended in such cases.

CTVA will also include the following structures:

- Iliac Lymphatic CTV= Internal iliac vessels + 1.0 cm symmetrical expansion.
- Presacral Lymphatic CTV = 8mm anterior to anterior border of sacral bone (extending from S1-S5)
- Mesorectal and perirectal lymphatic CTV
- Posterior border: anterior border of the sacrum and gluteus maximus
- Lateral border: Ileum, piriformis and obturator muscles
- Anterior border should overlap 1cm into the bladder, vagina or prostate.
- In the mid pelvis, this volume should include at least the posterior portion of the internal obturator vessels (which lie between the external and internal iliacs in the mid pelvis).

PTV-Conedown

CTV-B consists of the following structures that require a boost dose of radiation. A 0.5 cm uniform margin will be placed around the following structures to create PTV-Conedown. This volume will receive 5.4 Gy (1.8 Gy x 3).

- Primary tumor GTV

- Involved nodal GTV (if present)
- Presacral CTV (see above)

References:

RTOG Anorectal Contouring Atlas

<http://www.rtog.org/LinkClick.aspx?fileticket=DgflROvKQ6w%3d&tabid=231>

RTOG 0822 Protocol, Section 6 (Radiation Therapy)

<http://www.rtog.org/ClinicalTrials/ProtocolTable/StudyDetails.aspx?action=openFile&FileID=4663>

7.3.1.3 *Planning Constraints for IMRT Plans*

7.3.1.3.1 Normal Tissue Dose Constraints

The following normal structures must be contoured for each IMRT treatment plan:

- Small bowel, large bowel, sigmoid colon (contour up to 1cm above PTV)
 - ≤ 180 cc above 35 Gy
 - ≤ 100 cc above 40 Gy
 - ≤ 65 cc above 45 Gy
 - No small bowel volume should reach 50 Gy
- Bladder
 - $\leq 40\%$ above 40 Gy
 - $\leq 15\%$ above 45 Gy
 - No bladder volume should reach 50 Gy
- Femoral Heads
 - $\leq 40\%$ above 40 Gy
- Contour and Limit Dose as much as possible to the following structures:
 - Anal Sphincter
 - Female:
 - Uterus
 - Vagina
 - Male:
 - Prostate
 - Seminal Vesicles

7.3.1.3.2 PTV Planning Dose-Volume Constraints

- $\geq 98\%$ of PTV receives at least 93% of planned dose
- $\leq 10\%$ of PTV receives $\geq 105\%$ of prescribed dose
- $\leq 5\%$ of PTV receives $\geq 110\%$ of prescribed dose
- None of the PTV is to receive $\geq 115\%$ of prescribed dose

7.3.2 Image Guided Radiation Therapy (IGRT) for IMRT Plans

IGRT is optional in this trial. If used, IGRT should consist of daily CBCT or MVCT to bony pelvis with shifts made on kV port films to ensure that rectal markers and pelvis lymph nodes are covered with an adequate margin.

7.3.3 3-D Conformal Radiation Therapy (3-D CRT)

3-D CRT and/or tomotherapy 3-D plans will be permitted on this protocol for patients who have difficulty obtaining insurance coverage or have other issues that preclude the use of IMRT, although IMRT is preferred.

For designing 3-D fields, CTV, PTV, and OARs will be the same as those specified in the IMRT planning section (51). CTV and PTV must be delineated. Normal tissue dose constraints will also be the same. We recommend the following field borders for 3-D fields:

AP-PA field

Superior: L5-S1 interspace

Inferior: Ischial tuberosity

Lateral: 1-cm exterior to pelvic brim

Lateral field

Superior: L5-S1 interspace

Inferior: match to AP-PA fields

Anterior: Pubic symphysis; bowel may be excluded as long as there is a 1.5 cm margin around the PTV to ensure adequate coverage of this volume

Posterior: follow posterior curve of the sacrum to ensure complete coverage of the presacral space

Boost volumes

A 2-cm margin should be placed circumferentially on the primary GTV, involved nodal GTV, and presacral CTV to create the boost PTV. The field arrangement used to treat this target may be at the discretion of the treating radiation oncologist.

7.3.4 Treatment Break Outline

Pursuant with RTOG 0822: "Treatment interruptions are discouraged; however, they may be necessitated by uncontrolled diarrhea or other acute complications. The reason for and length of any such interruption must be documented. If the sum total of such interruptions exceeds 5 normally scheduled treatment days, this would constitute a major treatment violation. A minimum of 4 daily radiation therapy treatments are required in any given week. Any missed radiation treatments will be made up at the end of the treatment schedule, such that the total number of delivered 1.8 Gy fractions remains 28. If chemotherapy is held, radiation therapy will continue."

Toxicity	XRT Dose
Grade 2 thrombocytopenia	Continue at current dose.
Grade 3 thrombocytopenia	Hold until recovery to grade ≤ 1 , then resume.
Grade 4 thrombocytopenia	Hold until recovery to grade ≤ 1 (platelets $\geq 75 \times 10^9/L$), then resume.
Grade 3 neutropenia	Hold until recovery to grade ≤ 1 , then resume.
Grade 4 neutropenia	Hold until recovery to grade ≤ 1 , then resume.
Grade ≥ 3 febrile neutropenia	Hold until resolution of fever and neutropenia to grade ≤ 1 . Hold until the ANC $\geq 1,500/\text{mm}^3$ and fever has resolved. Then resume treatment.

References:

RTOG 0822 Protocol, Section 6 (Radiation Therapy)

<http://www.rtog.org/ClinicalTrials/ProtocolTable/StudyDetails.aspx?action=openFile&FileID=4663>

7.3.5 Capecitabine (Xeloda)

Capecitabine shall be delivered at $825\text{mg}/\text{m}^2$ BID during IMRT radiotherapy. Dose modification shall occur as follows:

- If $\text{ANC} < 1000/\text{mm}^3$ capecitabine will be held until the blood counts recover above these values and the patient can resume full dosing
- If platelet count $< 100,000/\text{mm}^3$, capecitabine will be held until the blood counts recover above these values and the patient can resume full dosing

Event Name	Hand-Foot Skin Reaction
Grade of Event	Management/Next Dose for Capecitabine
\leq Grade 1	No change in dose
Grade 2	Hold until \leq Grade 1. For the first appearance resume at 100% of the dose. For the second appearance, dose reduce to $650\text{ mg}/\text{m}^2$ For the third appearance, dose reduce to $500\text{ mg}/\text{m}^2$ For the fourth appearance, discontinue.
Grade 3	Hold until \leq Grade 1. For the first appearance, dose reduce to $650\text{ mg}/\text{m}^2$ For the second appearance, dose reduce to $500\text{ mg}/\text{m}^2$ For the third appearance, discontinue.
Grade 4	Hold until \leq Grade 1. For the first appearance, dose reduce to $500\text{ mg}/\text{m}^2$ For the second appearance, discontinue.

Event Name	Diarrhea
Grade of Event	Management/Next Dose for Capecitabine
\leq Grade 1	No change in dose
Grade 2	For the first appearance, dose reduce to $650\text{ mg}/\text{m}^2$ For the second appearance, dose reduce to $500\text{ mg}/\text{m}^2$ For the third appearance, discontinue. ¹
Grade 3	For the first appearance, dose reduce to $650\text{ mg}/\text{m}^2$ For the second appearance, dose reduce to $500\text{ mg}/\text{m}^2$ For the third appearance, discontinue. ¹

¹Capecitabine may be discontinued at the discretion of the investigator

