3. BACKGROUND

3.1 Rationale

Locally advanced rectal carcinoma continues to be a major oncologic problem in the United States with approximately 40,000 new cases diagnosed in 2012. For stage II/III rectal carcinoma, adjuvant chemoradiation (1-3) and total mesorectal excision (TME) (4, 5) represent the major treatment advances that have increased cure rates over the past 30 years.

In the setting of TME, a landmark phase III German trial of stage II/III rectal cancer patients established neoadjuvant 5FU-based chemoradiation (NCRT) as standard of care over the same regimen given post-operatively (6). The preoperative arm showed superior local control (6% vs. 13% p=0.006), a complete pathologic response of 8%, a higher rate of sphincter preservation and less grade 3 toxicity compared to post-operative treatment. However, disease-free and overall survival (76% versus 74%, respectively) were no different because of the high rate of distant metastasis occurring in over 1/3 of patients (5yr DM 36 vs 38%, p=0.84). Importantly, those attaining a pathologic complete response had a decreased rate of distant metastasis and improved disease-free survival. Drawbacks to the regimen include acute grade 3 or 4 toxicity in 27% of patients, low compliance rates with postoperative chemotherapy (27 – 50%), and an overall decline in anorectal function shown by long-term studies (6).

Given the excellent locoregional control reported in TME surgical series, several trials have investigated whether certain patients may be spared preoperative radiotherapy (7-9). Two large randomized trials by Dutch and British investigators showed that a short preoperative course of hypofractionated EBRT (25 Gy in 5 fractions) followed by TME surgery decreased locoregional recurrence by 2/3 as compared to patients treated with TME surgery alone. In the Dutch trial, patients with mid and distal rectal cancers were most likely to benefit from radiotherapy. In these patients, preoperative radiation was shown to decrease locoregional recurrence by 5-fold (10% to 2%); however, the

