7.5 Supportive Care

The following supportive care is recommended. However, it is ultimately at the discretion of the treating physician.

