7.5.2 Patients receiving External Beam Radiotherapy

Diarrhea, skin irritation, fatigue, urinary tract irritation, and decreased blood counts are the main side effects experienced during concurrent chemotherapy and pelvic radiation therapy. Standard supportive care measures may be used at the treating physician's discretion throughout the course of therapy, including antidiarrheal agents (loperamide, etc.), skin creams, and phenazopyridine (Pyridium). Specific guidelines for dose-reducing capecitabine as needed are given in Section 7.3.5.

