7.6 Subject Withdrawal/Removal

Patients will be removed from the study for the following reasons:

- Unacceptable toxicity from therapy. Toxicity must be appropriately documented.
- Development of intercurrent, non-cancer related illness that prevents either continuation of therapy or regular follow-up
- The patient decides to discontinue enrollment in the protocol at any time and for any reason
- Continuation of participation could be harmful
- Pregnancy
- The patient needs treatment not allowed in the study

All reasons for discontinuation of treatment must be documented.

- Patients who prematurely discontinue radiation treatment but undergo surgical exploration will be followed per the prescribed protocol schedule.
- Patients who prematurely discontinue radiation treatment and do not undergo surgical exploration will be followed for survival for five years.
- Patients who complete radiation treatment and do not undergo surgical exploration will be followed for survival for five years.

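### Capecitabine rules in 7.3.5: grade 3 diarrhea gets the same action as grade 2 with no hold, and the dose on resuming after a cytopenia hold is unclear

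*Combined protocol and SAP*

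**What the plan says.** Section 7.3.5 applies to the control arm only. It starts capecitabine at 825 mg/m² twice daily during radiotherapy and introduces the changes with "Dose modification shall occur as follows". Three sets of rules follow.

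- **Low counts.** For neutrophils below 1000/mm³ or platelets below 100,000/mm³, the two bullets share one ending: "capecitabine will be held until the blood counts recover above these values and the patient can resume full dosing". Nothing is said about a patient whose dose has already been cut for another toxicity.
- **Hand-foot reaction.** The rows for grades 2, 3 and 4 each begin with a hold until grade 1 or less. The dose afterwards depends on the grade. At grade 2: "For the first appearance resume at 100% of the dose". At grade 3 the first appearance leads to 650 mg/m², and at grade 4 to 500 mg/m².
- **Diarrhea.** The rows for grades 2 and 3 have identical text. Each opens "For the first appearance, dose reduce to" 650 mg/m², moves to 500 mg/m² at the second appearance and stops the drug at the third. Neither mentions a hold or a grade to which the diarrhea must recover. A footnote lets the investigator discontinue the drug.

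Section 7.5.2 states: "Diarrhea, skin irritation, fatigue, urinary tract irritation, and decreased blood counts are the main side effects experienced during concurrent chemotherapy and pelvic radiation therapy". It then refers the reader back to 7.3.5 for capecitabine reductions.

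**The concern.** The diarrhea table does not separate a moderate event from a severe one. In both cases the instruction is to lower the dose and carry on. The hand-foot table in the same section stops the drug first, for every grade above 1, and restarts it only after recovery. The protocol therefore applies a hold-and-recover principle to one capecitabine toxicity and not to the other, and gives no reason.

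The cytopenia wording raises a second, smaller question. A patient may already be on 650 or 500 mg/m² when the counts fall. Full dosing is not defined, so one site could restart that patient at 825 mg/m² and another at the reduced level.

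What is at stake is the safety of control-arm patients and consistent dosing across sites. Section 7.5.2 names both diarrhea and low counts as main side effects, so these rules cover expected events.

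**Working it through.** The plan gives no figure on this point to reproduce. The check is a comparison of texts plus simple dose ratios.

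**Step 1. The two tables side by side (both in 7.3.5).**

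| | Hand-foot, grade 2 | Hand-foot, grade 3 | Diarrhea, grade 2 | Diarrhea, grade 3 |
|---|---|---|---|---|
| Hold until grade 1 or less | yes | yes | no | no |
| First appearance | 100% | 650 | 650 | 650 |
| Second appearance | 650 | 500 | 500 | 500 |
| Third appearance | 500 | stop | stop | stop |
| Fourth appearance | stop | – | – | – |

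After the hold, the grade 3 dose steps match (650, 500, stop). What the diarrhea table lacks at grade 3 is the hold.

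**Step 2. Dose given during grade 3 diarrhea if the table is followed literally.**

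- First appearance: 650/825 = 0.788, so 79% of the starting dose, without interruption.
- Second appearance: 500/825 = 0.606, so 61%, again without interruption.

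**Step 3. Fixed doses when two toxicities occur.** A patient already on 650 mg/m² for hand-foot reaction who has a first grade 3 diarrhea is told to go to 650, so nothing changes. A patient already on 500 mg/m² meets a row that cannot be applied.

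**Step 4. Resuming after a cytopenia hold.**

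- If full dosing means 825 mg/m²: from 650, 825/650 = 1.269 (+27%); from 500, 825/500 = 1.650 (+65%).
- If it means the current dose level: 0%.

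The radiation table in 7.3.4 speaks of the current dose, so clearer wording was available within the protocol.

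**Step 5. What a hold would cost in capecitabine.** The course has 28 fractions (25 + 3, section 7.3.1.2). The documents do not say whether capecitabine is taken 5 or 7 days a week, so both are shown. Reduced doses are assumed to stay twice daily, and held doses are assumed not to be made up.

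- 5 days a week: planned course 825 × 2 × 28 = 46,200 mg/m². One week at 650 forgone: 650 × 2 × 5 = 6,500 mg/m², and 6,500/46,200 = 14.1%.
- 7 days a week: 28 fractions started on a Monday span 5 × 7 + 3 = 38 days, so 825 × 2 × 38 = 62,700 mg/m². One week at 650 forgone: 650 × 2 × 7 = 9,100 mg/m², and 9,100/62,700 = 14.5%.

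Each week held in place of 650 mg/m² thus removes about 14% of that patient's planned course.

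**The case against.** The strongest reply is that 7.3.5 should not be read alone. Section 11.8, whose side-effect lists are those of capecitabine, leaves changes to the chemotherapy regimen to the treating oncologists. Section 7.5.2 treats 7.3.5 as guidance for use when needed, and it sits under 7.5 Supportive Care, of which the protocol says "it is ultimately at the discretion of the treating physician". Section 7.3.4 foresees that chemotherapy may be held while radiation continues. The footnote permits discontinuation, 7.6 removes patients for "Unacceptable toxicity from therapy. Toxicity must be appropriately documented", and note 7 of the study calendar requires weekly toxicity checks during radiation. On this view an oncologist who holds capecitabine for grade 3 diarrhea is within the protocol. That stands, and it rules out the stronger inference that sites are compelled to keep dosing.

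It does not remove the defect. The footnote covers stopping for good and says nothing of a hold. Section 7.3.4 deals with radiation breaks. Weekly checks detect an event but do not say what to do about it. The one place that gives a specific instruction for grade 3 diarrhea omits the hold, under an introduction worded as mandatory.

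A second reply is that the diarrhea table is stricter than the hand-foot table at grade 2: it reduces at once and stops one appearance sooner. That is correct, and it is a reason to leave the grade 2 row as it is. It does not explain the missing hold at grade 3, where the dose steps are equal.

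A reader might also infer that the cytopenia bullets order re-escalation. They do not. The verb is permissive, and the clause can be read as part of the condition for ending the hold. The wording is ambiguous, and that is as far as the point goes.

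**Conclusion.** The point holds as a minor safety defect in a written control-arm rule. Taken literally, a first grade 3 diarrhea continues capecitabine at 79% of the starting dose with no hold and no recovery criterion. The cytopenia wording is a secondary ambiguity worth +27%, +65% or 0%, depending on the reading and on the dose already reached. Discretion elsewhere in the protocol lowers the practical risk and is why the point is minor.

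Three further inferences are not supported:

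- **Grade 4 diarrhea.** No such row appears in the text as read from the PDF, but tables may lose rows that way. Its absence cannot be counted as an omission.
- **How often this would occur.** Section 3.1 reports "acute grade 3 or 4 toxicity in 27% of patients", but that is all toxicity under a preoperative 5-FU regimen. The documents give no rate of grade 3 diarrhea with capecitabine, and nothing makes the 27% an upper limit for it. Nor is there a figure for patients who have both an earlier reduction and a later cytopenia.
- **Effect on the trial's result.** No sample size, power or test depends on these rules. Nothing in the documents links them to a change in pCR or in the comparison of arms.

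**What to change.** Make three edits in 7.3.5:

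1. Begin the grade 3 diarrhea row with *Hold until grade 1 or less* and keep its present doses. The grade 2 row can stay.
2. In both cytopenia bullets, replace the closing words on full dosing with *resume at the dose level in use before the hold*.
3. Add one sentence: *A reduced dose is not re-escalated; if rows conflict, the lower dose applies.* This also settles the rows in step 3 that change nothing or cannot be applied.

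How appearances are counted across grades is a clinical choice for the study oncologists.

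The cost is an amendment, which 13.1 requires the IRB to approve before use, and a memo to sites. No patients or visits are added, since toxicity is already reviewed weekly, and under 7.3.4 a capecitabine hold does not stop radiation. The real downside is lower capecitabine exposure in patients who are held, at the rate shown in step 5. The gain is limited to control patients still to be treated, and the documents do not say how many remain.
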